#### 1.4.2 Justification for Nivolumab 30-Minute Infusion

Long infusion times place a burden on participants and treatment centers. Using shorter infusion times of 30 minutes duration in participants will diminish the burden provided there is no change in safety profile. The US FDA has recently approved nivolumab 30-minute infusion with both 240 mg Q2W and 480 mg Q4W. Previous clinical studies show that nivolumab has been administered safely over 60 minutes at doses ranging up to 10 mg/kg over a long treatment duration. For example, in CA209010 (a Phase 2, randomized, double-blinded, dose-ranging study of nivolumab in participants with advanced/metastatic, clear cell RCC, N = 167), a dose association was observed for infusion site reactions and hypersensitivity reactions (5.1% at 0.3 mg/kg, 3.7% at 2 mg/kg and 18.5% at 10 mg/kg). All the events were Grade 1 - 2 and were manageable. The safety of nivolumab 3 mg/kg administered as a 30-minute infusion was

assessed in CA209153 in participants with previously treated advanced NSCLC. Overall, there were no clinically meaningful differences in the frequency of hypersensitivity/infusion-related reactions (of any cause or treatment-related) in participants administered nivolumab over a 30 minute infusion time compared with that reported for participants with the 60-min infusion time. An infusion duration of 30 minutes for nivolumab 480 mg (~ 60% of the dose provided at 10 mg/kg) is not expected to present any safety concerns compared to the prior experience at 10 mg/kg nivolumab dose infused over a 60-minute duration. Key safety results from the interim safety population of CA209511 (Part 2) demonstrate that the safety profile of nivolumab 480 mg IV over 30 minutes Q4W (N=142) is consistent with the established safety profile of nivolumab (3 mg/kg Q2W administered IV over 60 minutes) across multiple indications with respect to Grade 3-4 AEs, SAEs, AEs leading to discontinuation, and IMAEs including hypersensitivity/infusion reactions IMAEs. There were no new safety concerns identified. In addition, in Study CA017003, the Phase 1/2a trial of BMS-986205 combined with nivolumab, nivolumab was administered at doses of 240 mg Q2W and 480mg Q4W, both over 30 minutes, in combination with BMS-986205 given daily. There have been no signals of adverse tolerability with nivolumab given over 30 minutes at a dose of 480 mg Q4W in that study.

## 1.5 Combination of BMS-986205 and Nivolumab

Despite the overall impressive results of immune checkpoint inhibitors as therapeutic anti-cancer agents, clinical efficacy of PD-(L)1 pathway inhibition as a monotherapy has been limited to subsets of patients, with response rates of 20% or less in most tumor types. Additionally, many responsive patients eventually develop resistance to monotherapy, making combinatorial strategies attractive.

Preclinical and clinical data suggest that IDO may be a pathway contributing to primary and acquired resistance of PD-(L)1 inhibitors. Both pathways are up-regulated by interferon signaling suggesting that many PD-L1 positive tumors may also up-regulate IDO. Our data from clinical sarcoma samples confirms this (Figure 1) and others have demonstrated this in NSCLC[27]. Additionally, preclinical data and preliminary clinical reports have shown synergy of IDO inhibitors and immune checkpoint blockade[19]. Inhibition of IDO inhibition in combination with Ipilimumab in patients with advanced melanoma suggested potential improved overall response rates and PFS in immunotherapy-naïve patients compared to monotherapy (NCT01604889). Importantly, early reports also suggest the relative safety of combining IDO and checkpoint inhibition. A number of clinical trials are currently underway testing combinatorial strategies of IDO inhibitors plus CTLA-4 or PD-(L)1 inhibition in various tumors with promising results in preliminary reports.

[figure not shown]
Phase I/II study of the ECHO-202/KEYNOTE-037 trial showed that combination of IDO1 inhibitor (epacadostat) and pembrolizumab produced ORR of 56% and DCR of 71% in untreated melanoma patient. The median PFS was 12.4 months for all protocol patients. Response occurred in all subgroups including BRAF positive or negative tumor, normal vs elevated LDH, the

presence or absence of liver metastases. The most common adverse events were rash (46%), fatigue (43%), pruritus (29%), arthralgia (17%), diarrhea (15%), nausea (12%), increased AST (12%), increased lipase (11%), ALT increased (11%), and liver enzyme elevation (11-12%). However, only 4 patients (6%) discontinued the study due to adverse event[28].

In particular, the CA017-003 Phase 1/2a study reported that the maximum tolerated dose of BMS-986205 was 200 mg when combined with nivolumab, [24]. Anti-tumor activity was found during the dose expansion phase of BMS-986205 100mg among a group of heavily pre-treated bladder (25 patients) and cervical cancer patients (22 patients). In the bladder group, the objective response rate (ORR) was 32 percent (8/ 25 patients) and the disease control rate (DCR) was 44 percent (11/25 patients). In the cervical cancer cohort, ORR was 14 percent (3/ 22 patients) and DCR was 64 percent (14/22 patients). Patients with more than 1% of PD-L1 had ORR of 46% and 25% in bladder and cervical cancer respectively. The combination regimen was well tolerated with only 4 patients (1.4%) discontinuing from the study due to the drug toxicity. The most commonly reported adverse effect of any grade were fatigue (13.6%), nausea (11.5%), and decreased appetite (10.5%).

Given the success of immune checkpoint blockade in HCC, the existing data for synergistic effects with IDO inhibition and the known expression of IDO in HCC, we propose a phase I/IIa evaluating the safety and demonstrating the efficacy of BMS-986205 + nivolumab in unresectable HCC.

### Figure 1. Concordance of IDO1 and PD-L1 Expression in Human Sarcoma

## 1.6 Summary of Available Nonclinical and Clinical Data

Refer to the investigator's brochures for nivolumab and BMS-986205 for preclinical and clinical study data.

## 1.7 Correlative Studies

One of the major shortcomings of immunotherapy trials has been the lack of in depth correlative studies to help identify the mechanism of action, identify biomarkers of response, and explain the mechanisms governing treatment response or failure. To address this we plan to perform in depth immunological analysis of patient blood and tumor samples. This study incorporates serial tissues samples pre-treatment, during therapy and at progression (optional). The design of this study allows us to compare immune mechanisms pre-, on- to post-therapy.

Tumor PD-L1 expression has been linked to response rates of PD-1 checkpoint blockade [29]. Additionally, little is known about how the pattern of expression (i.e., tumor cells vs. infiltrating immune cells) affects response. Data presented at ASCO and SITC meetings indicate that durvalumab monotherapy response rates in NSCLC are 27% in PD-L1 positive tumors and 5% in PD-L1 negative tumors. TILs and a T-cell inflamed phenotype have been linked with response to CTLA-4 checkpoint blockade in melanoma [30, 31]. Exclusion of T-cells in the tumor microenvironment has also been linked with lack of response to checkpoint inhibition [32] with down-regulation of CCL4 mediated dendritic cell recruitment as one potential mechanism [32]. Whether PD-L1 expression or the presence of TILs is important for response to IDO inhibitors is unknown.

Mutational burden and antigenic load are thought to represent a surrogate for tumor antigenicity and have been linked with response to checkpoint blockade in NSCLC [34]. Whether mutational load is true indicator of tumor antigenicity and how this correlates with response to IDO inhibitors is unknown. To address this we plan to perform in depth immunological analysis of patient blood and tumor samples. We will evaluate immunologic changes systemically and in the tumor and tumor microenvironment within patient's pre to post therapy and across the cohort of patients to identify predictive biomarkers and elucidate the mechanistic immunologic effects of therapy.

## **2.0 STUDY OBJECTIVES**

### **2.1 Primary Objective**

1. To obtain the safety and tolerability of BMS-986205 in combination with nivolumab in unresectable / metastatic HCC in the first or second line setting using CTCAE V5.0 criteria.
2. To determine efficacy as defined by objective response rate (ORR) of BMS-986205 in combination with nivolumab in unresectable / metastatic HCC in the first or second line setting using RECIST (version 1.1).

### **2.2 Secondary Objectives (Phase II)**

1. To determine disease control rate (DCR), duration of response (DOR), progression free survival (PFS), and overall survival (OS) by RECIST 1.1 and ORR using immune RECIST (iRECIST) of BMS-986205 in combination with Nivolumab in unresectable HCC.
2. To further evaluate safety of BMS-986205 in combination with Nivolumab in unresectable HCC.

### **2.3 Correlative Objectives**

1. To analyze serial blood samples for serum cytokine and tryptophan / kynurenine levels, and to quantify the number, function, and gene expression of peripheral blood mononuclear cells (PBMCs).
2. To evaluate serial tumor tissue biopsies for tumor infiltrating immune cell subsets, expression of immune regulatory proteins including IDO1 and PD-L1, gene expression signatures, and mutational load.
3. To evaluate pre-treatment stool samples for microbiome signatures
4. To explore potential biomarkers

### 3.0 STUDY DESIGN

This is a phase I/II study using a Simon optimal two stage design for efficacy of BMS-986205 in combination with nivolumab as illustrated in the schema. For the phase I portion the primary endpoint is to determine safety profile of BMS-986205 in two dose levels with nivolumab in unresectable HCC using CTCAE V5.0 criteria. For the phase II portion the primary endpoints are safety and toxicity and the objective response rate using the using RECIST criteria. Exploratory endpoints include disease control rate (DCR), duration of response (DOR), ORR using iRECIST, progression free survival (PFS), overall survival (OS), and correlative studies.

For phase I dose escalation, up to two dose levels of BMS-986205 will be evaluated: 50 mg daily and 100mg daily. These two dose levels were selected based on the clinical data described above. We have chosen 50 mg daily as the starting dose level given the existing safety data for this dose and the safe use of this dose in use with other immunotherapy combinations. The dose of BMS-986205 will be escalated to 100 mg daily if 0 of the first 3 patients experience a dose limiting toxicity (DLT) at 50 mg BMS-986205. Three additional patients will be added to receive 50 mg BMS-986205 if 1 of the first 3 patients experiences a DLT. The dose of BMS-986205 will be escalated to 100 mg daily if no more than one of six patients experience a DLT at 50 mg BMS-986205. The expansion phase will be conducted after MTD is reached, which will be defined as no more than one of six patients develops a DLT at 50 mg or 100 mg of BMS-986205 daily with nivolumab. If BMS-986205 50mg daily is not tolerated the study will be halted and modified after discussion with the principal investigator (PI) and BMS. The 6 patients at the maximum tolerated dose in the phase I portion treated at MTD will count towards the 17 patients needed in the phase II expansion cohort. The phase II cohort will be run as a Simon two-stage design to allow for early trial stoppage for futility. We designate an ORR as defined by RECIST criteria of 5% as not worthy of further investigation and of 25% as worthy of further investigation. In the first stage 9 patients will be accrued and at least 1 response must be observed within 6 months of treatment (or longer at PI discretion) to continue the trial (n1=9, r1=0) (see study schema). BMS-986205 will be administered orally daily and nivolumab will be administered intravenously until disease progression.

Toxicity will be assessed using the NCI CTCAE, version 5.0 unless otherwise specified. A DLT is defined (See section 5.6) as any of the following that occur during the 56-day DLT period.

If subjects cannot receive 75% of intended dose of BMS-986205 for reasons other than toxicity and did not experience a DLT, they will be replaced for DLT assessment. Subjects treated at MTD will be monitored for chronic toxicity for 3 months to determine a recommended Phase 2 dose (RP2D).

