## Phase II Dose Expansion (Simon Two-stage) Design

17 patients including those from Phase 1 at MTD

P0=0.05, p1=0.20, r1=1, n1=16, rTot=3, nTot=30,  $\alpha=0.05$ , power=0.8

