### 1.2 Hepatocellular Carcinoma

Hepatocellular carcinoma (HCC) is a leading cause of cancer-related death worldwide and US and incidence of HCC is rising and estimated 782,000 new cases per year worldwide[3]. Surgery is the mainstay of therapy for early stage disease but due to medical comorbidities or advanced disease many patients are not candidates for surgical resection or liver-directed therapies and effective and tolerable systemic treatment options are desperately needed[4]. The only first line systemic therapy is sorafenib, a multi-targeted tyrosine kinase inhibitor (TKI) with moderate overall survival (OS) of 3 months over supportive care with commonly intolerable side effects[5]. Regorafenib, another multi-targeted TKI was recently approved in the second-line setting with median OS 10.6 months compared to 7.8 months with placebo[6]. Nivolumab has recently been approved in patients with unresectable HCC, refractory to sorafenib, as second line therapy with the objective response rate of 20%[7].

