The HCC tumor microenvironment has been shown to have an abundance of immunosuppressive factors and the correlation between the presence of tumor infiltrating lymphocytes and outcomes present an opportunity for immunotherapeutic approaches in this disease setting[26]. PDL-1 overexpression is shown to have poor prognosis in HCC. The safety and efficacy of nivolumab were evaluated in a phase 1/2 dose escalation and expansion trial in patients with advanced HCC among whom a majority of patients had progressed on prior sorafenib [7]. In that study, 48 patients participated in a dose escalation phase (which allowed Child-Pugh score (CP) of 7 or less) and 214 patients were treated in the dose expansion phase limited to patients with CP 6 or less. The objective response rate was 15% in dose-escalation phase and 20% in dose expansion phase. Interestingly, patients with no prior therapy experienced better objective response of 23% and 9 month overall survival of 82%. Transient reduction in HCV RNA was observed in some patients and no viral reactivation was reported in the study.

Any grade and grade 3/4 treatment-related adverse were reported in sixteen (7%) and nine (4%) patients respectively. Grade 3/4 adverse events were observed as AST increase in nine (4%), ALT increase in five (2%), diarrhea in three (1%) and fatigue in three (1%).

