## 4.0 SUBJECT SELECTION

### 4.1 Inclusion Criteria

Patients must meet all of the following criteria to be eligible for study entry.

1. Men and women  $\geq 18$  years of age at the time of study entry.
2. Willing and able to provide written informed consent for the trial.
3. Life expectancy  $>12$  weeks.
4. Histologically or imaging confirmed hepatocellular carcinoma (mixed hepatocellular/cholangiocarcinoma or fibrolamellar subtypes are excluded).
5. Have disease that is not amenable for curative treatment approach.
6. Have measurable disease based on RECIST v1.1.
7.  $\geq 1$  liver lesions accessible for core biopsy that was either not previously treated by liver-directed therapy or progressed following liver-directed therapy.
8. Child-Pugh score of A.
9. ECOG performance status of 0 or 1.
10. Adequate hematology parameters:
  - a. Absolute neutrophil count (ANC)  $\geq 1000$  cell/mm $^3$
  - b. Platelet count  $\geq 50,000$ /mm $^3$
  - c. Hemoglobin (Hgb)  $\geq 8$  g/dL
11. Acceptable blood chemistry levels:
  - a. AST/SGOT, ALT/SGPT  $\leq 5$  x upper limit of normal (ULN)
  - b. Total bilirubin  $\leq 2$  ULN
  - c. Creatinine  $\leq 2$  x ULN
12. Subjects with active hepatitis B virus (Hep B) are allowed if antiviral therapy for hepatitis B has been given for  $>8$  weeks and viral load is  $<100$  IU/ml prior to first dose of trial treatment. Subjects with untreated hepatitis C virus (HCV) are allowed.
13. Willingness to undergo mandatory pre-treatment biopsy (unless there is adequate archival tumor specimen available) and mandatory on-treatment biopsy.

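### The efficacy rule tests the combination against a 5% response rate, although the protocol cites 15–23% for nivolumab alone; an inert add-on would still meet it with probability 0.46–0.76

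*Combined protocol and SAP*

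**What the plan says.** Section 3.0 sets the null: "We designate an ORR as defined by RECIST criteria of 5% as not worthy of further investigation". The rate worth pursuing is 25%. Sections 14.1 and 14.2 and the synopsis give the rule and its properties. Nine patients are treated at the MTD, and accrual continues if at least one responds. The treatment goes forward if at least 3 of 17 respond and safety is acceptable. The claimed properties are 80% power at a one-sided 0.05 level.

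The background gives the activity of nivolumab on its own in this disease. Section 1.4: "The objective response rate was 15% in dose-escalation phase and 20% in dose expansion phase", and "patients with no prior therapy experienced better objective response of 23" per cent. Section 1.2 describes the approval of nivolumab after sorafenib "as second line therapy with the objective response rate of 20" per cent. On the populations, Section 1.4 says "214 patients were treated in the dose expansion phase limited to patients with CP 6 or less", while the escalation phase allowed a score of 7. This trial requires a "Child-Pugh score of A" (Section 4.1), which Appendix 6 defines as 5–6 points, and it enrols first- and second-line patients.

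The study schema prints another design with the same null: "P0=0.05, p1=0.20, r1=1, n1=16, rTot=3, nTot=30".

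**The concern.** The null rate in a two-stage design should be one at which the regimen would not merit further work. Here the regimen contains a drug that the protocol itself reports as producing responses in 15–23% of such patients, and Section 1.5 bases the case for the trial partly on "the existing data for synergistic effects with IDO inhibition". A null of 5% lies below every cited nivolumab-alone rate, and no section explains the choice.

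Overall response rate is a primary endpoint, and the 3-of-17 rule decides whether the combination is called worthy of further study. A reader who sees a one-sided 0.05 level could take it as the risk of advancing an inactive add-on. It is not: it is the risk of passing when the whole regimen, nivolumab included, has a 5% response rate. The safety and correlative aims are not affected.

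**Working it through.** **Inputs.** Stage 1 has n1 = 9 and continues with at least 1 response; the final rule is at least 3 of 17 (Sections 3.0 and 14.1). The null is 5% and the target 25% (Sections 3.0 and 14.2). Nivolumab-alone rates are 15%, 20% and 23% (Section 1.4).

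**Formula.** With X1 ~ Bin(9, p) and X2 ~ Bin(8, p):

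P(criterion met) = P(X1 = 1)·P(X2 ≥ 2) + P(X1 = 2)·P(X2 ≥ 1) + P(X1 ≥ 3)

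P(stop at stage 1) = (1 − p)^9

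**Reproducing the plan's figures.** At p = 0.05: 0.2985 × 0.0572 + 0.0629 × 0.3366 + 0.0084 = 0.0466, within the 0.05 limit. At p = 0.25 the result is 0.812, consistent with 80% power. An exhaustive search confirms that this is the optimal Simon design for 5% against 25%. Its expected size under the null is 9 + 8 × (1 − 0.630) = 11.96 patients. The design is computed correctly for the hypotheses it states.

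**If BMS-986205 adds nothing.** The true rate is then the nivolumab-alone rate. At p = 0.20:

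- P(X1 = 1) = P(X1 = 2) = 0.3020, and P(X1 ≥ 3) = 0.2618
- P(X2 ≥ 2) = 0.4967, and P(X2 ≥ 1) = 0.8322
- 0.3020 × 0.4967 + 0.3020 × 0.8322 + 0.2618 = 0.663

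| True response rate | Origin | Stops at 0/9 | Criterion met |
|---|---|---|---|
| 5% | plan's null | 0.630 | 0.047 |
| 10% | assumption: half the cited 20% | 0.387 | 0.223 |
| 15% | nivolumab, escalation | 0.232 | 0.456 |
| 20% | nivolumab, expansion | 0.134 | 0.663 |
| 23% | nivolumab, no prior therapy | 0.095 | 0.760 |
| 25% | plan's target | 0.075 | 0.812 |

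The probability of meeting the criterion reaches 0.10 at a true rate just under 6.9%. The nivolumab-alone rate here would have to be no higher than that for the risk to stay at or below 0.10.

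**What a minimal pass shows.** The observed rate is 3/17 = 17.6%, below the cited 20%. The exact 95% confidence interval planned in Section 14.3 would be 3.8% to 43.4%, which covers the whole 15–23% range.

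**The schema design.** This reads the printed r values in the usual Simon way: stop at 1 or fewer of 16, succeed at 4 or more of 30. That reading is an assumption, but it reproduces the printed alpha (0.048) and power (0.807). The schema's acceptable rate of 20% equals the cited nivolumab expansion rate, so its power is the chance of success at that rate. At 15% and 23% the probabilities are 0.594 and 0.884. Sections 3.0 and 14.1 do not use this design, although Section 3.0 refers the reader to the schema.

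**The case against.** The strongest reply is that the plan tests what it says it tests. The objective is the response rate of the combination, the 5% and 25% values are printed openly, and passing means only that further study is warranted. The protocol nowhere claims that 3 of 17 shows superiority to nivolumab, and a small single-arm trial cannot isolate an add-on's contribution. All of this is true. It is a reason to keep the rule and limit the claim. It does not supply the missing justification for 5%, nor does it tell the reader how often an inert add-on would pass.

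A second reply is that the benchmark is soft, and this too stands in part. The 15% cohort allowed a Child-Pugh score of 7, and the 23% figure is for patients with no prior therapy, whereas this trial mixes lines. The closest single figure is therefore 20%, giving 0.66, with 15% and 23% as sensitivity values. Section 4.2 does not exclude prior PD-1 therapy, which could lower the nivolumab-alone rate here. Section 1.4 does not say whether its responses were confirmed, and Section 14.1 does not say whether the 3 of 17 must be. None of this is offered in the documents as a reason for 5%, and even at half the cited 20% the criterion is met with probability 0.22.

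Third, the planned confidence interval and the separate reporting of confirmed responses (Section 11.5.3.3) give a careful reader some protection. They do not change what the go rule is said to show.

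Finally, the schema mismatch is a separate inconsistency, and the case against the 5% null does not depend on it.

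**Conclusion.** The concern holds. The design is correct as a test of the combination against 5%, but 5% is unexplained and lies below every nivolumab-alone rate the protocol cites. At the closest cited benchmark, 20%, an add-on with no effect would meet the efficacy criterion with probability 0.66; the range over 15–23% is 0.46 to 0.76. At 20–23% that is close to the 0.81 achieved at the target, so the rule barely separates a useful add-on from an inert one. The 0-of-9 step gives little protection, stopping 13% of such trials at 20%.

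The figures assume that the cited rates apply to the patients enrolled and that responses are counted in a comparable way. They exclude the unquantified safety proviso, so they are upper bounds on the full go decision. This should be fixed. It concerns how the efficacy result is interpreted, not the conduct of the trial.

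**What to change.** Keep the 17 patients, the 0-of-9 step and the 3-of-17 rule. Amend Sections 3.0, 14.1 and 14.2 and the synopsis as follows:

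1. State that 3 or more responses in 17 supports only the conclusion that the combination's response rate exceeds 5%, and is not by itself evidence that adding BMS-986205 improves on nivolumab.
2. Beside the alpha and power, print the probability of meeting the efficacy criterion at true rates of 15%, 20% and 23%: 0.46, 0.66 and 0.76.
3. Pre-specify that the response rate and its exact 95% confidence interval will be reported next to the cited nivolumab-alone rates (15–23%, main figure 20%) as descriptive context. Note that comparability is uncertain because of possible prior PD-1 therapy and unclear response confirmation.

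At the same time, reconcile the schema's parameter line with the 9/17, 5% against 25% design in Sections 3.0 and 14.1.

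The cost is a wording amendment, with no extra patients and no change to the decision rule. The drawback for the sponsor is a less favourable stated claim.
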